#### 9.4. Deaths, Serious Adverse Events and Other Significant Adverse Events

The number and proportion of participants reporting an SAE will be presented by treatment group, MedDRA SOC, HLTG, PT, and relationship to study product for participants enrolled before Protocol v11.0 (**Table 48**) and for participants enrolled under Protocol v11.0 (**Table 49**).

Individual data listings of deaths and other SAEs will be provided for participants enrolled prior to Protocol v11.0 (**Table 52**) and for participants enrolled under Protocol v11.0 (**Table 53**). These listings will include participant ID, treatment group, AE description, SOC, HLTG, PT, duration of AE, reason reported as an SAE,

severity, relationship to treatment, alternate etiology if not related, action taken with study treatment, whether the participant discontinued due to the AE, and AE outcome.

Individual listings of SUSARs ([Table 58](#) and [Table 59](#)) and UPs ([Table 60](#) and [Table 61](#)) will also be presented for participants enrolled prior to Protocol v11.0 and for participants enrolled under Protocol v11.0, respectively. These listings will include participant ID, treatment group, AE description, SOC, HLG7, PT, duration of AE, severity, relationship to treatment, alternate etiology if not related, action taken with study treatment, whether the participant discontinued due to the AE, and AE outcome.

## 9.5. Pregnancies

For any participants in the Safety Population who become pregnant during the study, every attempt will be made to follow these participants until the immediate postnatal period (6 weeks) or until termination or loss of the pregnancy to document the outcome, including information regarding any complications with pregnancy and/or delivery. Individual data listings of pregnancy reports will be provided if a pregnancy occurs post dosing:

- Maternal information will be presented in [Listing 28](#).
- Gravida and para information will be presented in [Listing 29](#).
- Live birth outcomes will be presented in [Listing 30](#), and still birth outcomes will be presented in [Listing 31](#).
- Spontaneous, elective, or therapeutic abortion outcomes will be presented in [Listing 32](#).

## 9.6. Clinical Laboratory Evaluations

Descriptive statistics for clinical laboratory test results including changes from baseline will be presented by time point and treatment group. Baseline is defined in [Section 3.3](#). Laboratory results obtained after start of dosing will be graded according to toxicity grading criteria given in [Table 5](#) and [Table 6](#) for participants who screened and enrolled prior to Protocol v11.0 and according to NCI CTCAE, Version 5.0 – November 2017 for participants who screen and enroll with Protocol v11.0. Note there are two instances in which the NCI CTCAE, Version 5.0 will not be used as implied: (1) eGFR toxicity will be assessed via chronic kidney disease, not acute kidney injury; and (2) calcium (corrected for albumin) will not be used and general grading (CTCAE term Investigations - Other) will be used instead. Laboratory results will be summarized by toxicity grade separately for participants who enrolled prior to Protocol v11.0 and participants who enrolled under Protocol v11.0.

Laboratory results that meet grading criteria per the toxicity table but fall within the specific site's reference range may be recorded in the database as normal and will only be reported as an AE if deemed related or clinically significant per the site PI. Any laboratory results that meet this criteria will be described in the CSR.

All safety laboratory results, change from baseline, and severity with applicable references ranges will be listed for each parameter by treatment group and time point. Unscheduled clinical laboratory evaluations will be included in listings of all clinical laboratory results but excluded from tabular and graphical summaries by time point, except when calculating the maximum severity post baseline. Abnormal laboratory results will also be presented. Abnormal laboratory results that do not have toxicity grading ranges defined will not have severity indicated in tables and listings except as “ONR” (outside of normal range). Abnormal laboratory results for parameters with defined toxicity grading ranges that are outside of the normal range but not at least mild in severity will have ONR as the severity included after the result.

The sort order for chemistry parameters will be as follows: sodium, potassium, bicarbonate, glucose, blood urea nitrogen, creatinine, eGFR, calcium, albumin, total protein, AP, AST, ALT, direct bilirubin, total bilirubin, and cystatin-C.

The sort order for hematology parameters will be as follows: hemoglobin, WBC, lymphocytes, neutrophils, eosinophils, platelets, hematocrit, RBC, basophils, and monocytes.

The sort order for coagulation parameters will be as follows: APTT, prothrombin time, and INR.

The sort order for urinalysis parameters will be as follows: urine protein, urine glucose, bilirubin, nitrite, occult blood, urine WBC, urine RBC, urobilinogen, ketones, and leukocyte esterase.

- All chemistry results, including at unscheduled visits, will be presented in [Listing 15](#). Abnormal chemistry results, including ONR and Grade 1 or higher results, will be presented in [Table 62](#) for participants enrolled prior to Protocol v11.0 and in [Table 63](#) for participants who enrolled under Protocol v11.0.
- All hematology results, including at unscheduled visits, will be presented in [Listing 16](#). Abnormal hematology results, including ONR and Grade 1 or higher results, will be presented in [Table 64](#) for participants enrolled prior to Protocol v11.0 and in [Table 65](#) for participants who enrolled under Protocol v11.0.
- All coagulation results, including at unscheduled visits, will be presented in [Listing 17](#). Abnormal coagulation results, including ONR and Grade 1 or higher results, will be presented in [Table 66](#) for participants enrolled prior to Protocol v11.0 and in [Table 67](#) for participants who enrolled under Protocol v11.0.
- All urinalysis results, including at unscheduled visits, will be presented in [Listing 18](#). Abnormal urinalysis results, including ONR and Grade 1 or higher results, will be presented in [Table 68](#) for participants enrolled prior to Protocol v11.0 and in [Table 69](#) for participants who enrolled under Protocol v11.0.

All screening results will be listed for each participant by treatment group and visit. Serology results will be presented in [Listing 19](#), serum  $\beta$ -hCG and FSH pregnancy testing results will be given in [Listing 20](#), and urine toxicology and alcohol results will be presented in [Listing 21](#).

The distribution of laboratory results will be presented by severity, treatment group, and time point.

## Chemistry

- Proportions of participants with mild, moderate, and severe results for any chemistry parameter will be presented for participants who enrolled prior to Protocol v11.0 in [Table 70](#) by treatment group, severity at baseline, time point, and severity across all graded chemistry parameters. Proportions of participants with results that are mild, moderate, severe, life-threatening, or result in death for any chemistry parameter will be presented for participants who enrolled under Protocol v11.0 in [Table 71](#) by treatment group, severity at baseline, time point, and severity across all graded chemistry parameters.
- Proportions of participants with graded abnormal results will be presented by treatment group, severity at baseline, time point, and severity separately for participants enrolled prior to Protocol v11.0 and for participants enrolled under Protocol v11.0 for chemistry parameters beginning in [Table 72](#) and continuing through [Table 101](#). Chemistry parameters with separate high and low toxicity ranges will be summarized by severity with high and low ranges indicated. The

proportions of participants with ONR results will be presented by treatment group, severity at baseline, time point, and severity for chemistry parameters that do not have toxicity grading ranges defined in **Table 102** and **Table 103**.

- Proportions of participants with graded CS chemistry results post-baseline will be presented by parameter, treatment group, and maximum severity of all CS results post-baseline for participants enrolled prior to Protocol v11.0 in **Table 120** and for participants enrolled under Protocol v11.0 in **Table 121**. The proportions of participants with CS ONR chemistry results post-baseline will also be presented by parameter, treatment group, and maximum severity of all CS results for parameters that do not have toxicity grading ranges defined in **Table 122** for participants enrolled prior to Protocol v11.0 and in **Table 123** for participants enrolled under Protocol v11.0.

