- 12-lead ECG: subjects will be asked to rest supine for at least 5 minutes prior to ECG.
  - TriPLICATE ECGs with 10-second rhythm strips will be obtained within a 60-minute period prior to dosing and within approximately 15 minutes after dosing is complete, separated by at least 1 minute.
  - Single, standard 12-lead safety ECGs will also be obtained.
  - All ECG recordings will be taken before obtaining any blood sample.
  - Significant changes are defined as the following:
    - Any significant change in rate or rhythm as determined by the site PI
    - QTcF interval of greater than 450 msec (male) or greater than 470 msec (female)
    - Increase from the QTcF baseline (defined as mean of pre-dose measurements) greater than 50 msec until the change resolves.

If any of these changes are observed, triPLICATE ECG tracings, approximately 2 minutes apart, should be recorded and repeated hourly until cessation of the abnormality.

---

- Reader will sign and date the safety ECGs and provide a global interpretation using the following categories:
  - Normal
  - Abnormal—not clinically significant (NCS)
  - Abnormal—CS
- Clinically significant ECG findings with new onset (or change in severity or frequency) any time after the administration of study product will be recorded as AEs. Clinical significance of ECG findings will be determined by the site PI based on his/her overall interpretation of data. Original ECG tracings will be retained as source documentation in the subject's records at the clinical site.
- During the study, from 30 minutes before the administration of study product until approximately 4 hours post dose, continuous 12-lead ECG remote telemetry monitoring will be conducted to assess for acute changes. If a CS change occurs, the monitoring will be continued until it has resolved and it is deemed safe to discontinue monitoring by the site PI or designee.

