#### **3.2. Endpoints**

##### **3.2.1. Primary**

- Occurrence of adverse events (AEs) and serious adverse events (SAEs) following the start of study product administration through the final visit (Day 150 [ $\pm 7$ ]), or Early Termination (ET).
- The occurrence of clinically significant (CS) changes from baseline in vital signs and clinical safety laboratory values following administration of study product through final visit (Day 150 [ $\pm 7$ ]), or ET.
- The occurrence of CS changes in electrocardiogram (ECG) parameters post administration of study product through the final visit (Day 150 [ $\pm 7$ ]), or ET.

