## 9.8.      **Electrocardiograms**

Standard 12-lead ECGs will be performed at Screening (in triplicate), Day 1 prior to dosing, Day 4, final study visit (Day 150), and ET visits. Unscheduled 12-lead ECG measurements will be listed but excluded from tabular and graphical summaries by time point. Individual ECG measurements, overall interpretations, and abnormal findings will be presented in **Listing 24**, **Listing 25**, and **Listing 26**, respectively.

Clinical significance for post-dose ECGs will be determined by the site PI with consideration to persistence, association with clinical symptoms, and impact to participant safety. For all participants, clinically significant ECG parameters will include any results meeting toxicity grading criteria (using **Table 4** for participants who screened and enrolled prior to Protocol v11.0 or NCI CTCAE, Version 5.0 for participants who screened and enrolled with Protocol v11.0) who had an overall ECG interpretation of abnormal, clinically significant.

The sort order for ECG parameters will be as follows: PR interval, QRS duration, QT interval, QTcF correction, RR interval, and ventricular rate.

12-lead standard ECG results will be summarized in the following tables and figures:

- Change in overall interpretations of post-dose 12-lead standard ECG results from baseline will be summarized by treatment group and time point in **Table 221**.
- Descriptive statistics for each ECG parameter and its change from baseline, including mean, SD, median, min, and max, will be presented by treatment group and planned time point in **Table 222**.
- Mean change from baseline of ECG parameters will also be presented with bars representing  $\pm 1$  SD by treatment group and planned time point beginning in **Figure 52** and continuing through **Figure 57**.

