**Tables with Similar Format (continued):**

**Table 111:** Laboratory Summary Statistics by Time Point and Treatment Group for the Safety Population – Calcium (mg/dL)

**Table 112:** Laboratory Summary Statistics by Time Point and Treatment Group for the Safety Population – Albumin (g/dL)

**Table 113:** Laboratory Summary Statistics by Time Point and Treatment Group for the Safety Population – Total Protein (g/dL)

**Table 114:** Laboratory Summary Statistics by Time Point and Treatment Group for the Safety Population – Alkaline Phosphatase (U/L)

**Table 115:** Laboratory Summary Statistics by Time Point and Treatment Group for the Safety Population – AST (U/L)

**Table 116:** Laboratory Summary Statistics by Time Point and Treatment Group for the Safety Population – ALT (U/L)

**Table 117:** Laboratory Summary Statistics by Time Point and Treatment Group for the Safety Population – Direct Bilirubin (mg/dL)

**Table 118:** Laboratory Summary Statistics by Time Point and Treatment Group for the Safety Population – Total Bilirubin (mg/dL)

**Table 119:** Laboratory Summary Statistics by Time Point and Treatment Group for the Safety Population – Cystatin-C (mg/L)

**Table 120: Clinically Significant Graded Chemistry Results by Maximum Severity Post-Baseline, Parameter, and Treatment Group for Participants in the Safety Population Enrolled Prior to Protocol v11.0**

[Implementation Note: Repeat for the following treatment groups: All Participants, SAR440894 0.3 mg/kg, SAR440894 1 mg/kg, SAR440894 3 mg/kg, SAR440894 10 mg/kg, SAR440894 20 mg/kg, and Placebo.

The table will include the following parameters: Sodium (High), Sodium (Low), Potassium (High), Potassium (Low), Bicarbonate (High), Bicarbonate (Low), Glucose High), Glucose (Low), Blood Urea Nitrogen, Creatinine, eGFR, Calcium (High), Calcium (Low), Albumin, Total Protein, Alkaline Phosphatase, AST, ALT, Direct Bilirubin, and Total Bilirubin.]

Parameter	Treatment Group	N	Mild / Grade 1		Moderate/ Grade 2		Severe/ Grade 3	
			n	%	n	%	n	%
Sodium (High)	All Participants	x	x	xx	x	xx	x	xx
	SAR440894 0.3 mg/kg							
	...							
	Placebo							
Sodium (Low)	All Participants							
	SAR440894 0.3 mg/kg							
	...							
	Placebo							
Potassium (High)	All Participants							
	SAR440894 0.3 mg/kg							
	...							
	Placebo							
...	...							

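### The by-parameter tables of clinically significant laboratory results have no cell for a result that carries no toxicity grade on a parameter that has a grading scale

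*SAP*

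**What the plan says.** SAP 3.2.1 defines the second primary endpoint as: "The occurrence of clinically significant (CS) changes from baseline in vital signs and clinical safety laboratory values". The third is separate: "The occurrence of CS changes in electrocardiogram (ECG) parameters post administration of study product". Neither mentions a toxicity grade.

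SAP 9.6 sends CS laboratory results to by-parameter tables along two routes.

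- **Parameters with a grading scale.** "Proportions of participants with graded CS chemistry results post-baseline will be presented by parameter, treatment group, and maximum severity of all CS results post-baseline". Hematology, coagulation and urinalysis are worded alike. The shells for participants enrolled before v11.0 (Tables 120, 156, 171, 198) have columns for Grades 1 to 3. Those for participants under v11.0 (121, 157, 172, 199) have Grades 1 to 5.
- **Parameters without a scale.** CS out-of-range results are shown by maximum severity "of all CS results for parameters that do not have toxicity grading ranges defined". The shells cover cystatin-C (122-123), hematocrit, RBC, basophils and monocytes (158-159), and ketones and leukocyte esterase (200-201). Coagulation has no such table.

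SAP 9.6 also foresees the case in between. "Abnormal laboratory results for parameters with defined toxicity grading ranges that are outside of the normal range but not at least mild in severity" are to be labelled ONR (outside normal range).

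The parameter list of the graded chemistry shell, Table 120, ends "Alkaline Phosphatase, AST, ALT, Direct Bilirubin, and Total Bilirubin". Vital-sign Tables 219-220 have grade columns only.

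For ECG, SAP 9.8 first leaves clinical significance to the site PI. It then says that "clinically significant ECG parameters will include any results meeting toxicity grading criteria", provided the overall reading is also abnormal and CS. Protocol 7.1 says "Clinical significance of ECG findings will be determined by the site PI".

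**The concern.** The endpoint turns on an investigator's judgement that a change is clinically significant. The by-parameter tables add a second condition, a grade, whenever the parameter has a scale. A result that is flagged CS, out of range and ungraded fits neither route: the first has no column for it and the second excludes its parameter.

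These are the tables from which a reader learns which test was affected, in which dose group and how severely. With 6 active participants per dose and 10 pooled placebo, each split by protocol version, one missing participant is visible. The any-CS-laboratory count in Tables 40/41 could then exceed what the parameter tables can account for, with nothing in those tables to explain the difference.

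**Working it through.** The plan states no figure to reproduce: sample size was not derived from a hypothesis and the endpoint is descriptive. The check traces the routes through the shells and counts how often the scale leaves a direction ungraded.

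**1. Where an ungraded CS result on a scaled parameter would appear**

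| Display | Has a place for it? |
|---|---|
| Tables 120-121, 156-157, 171-172, 198-199 (by-parameter CS, graded) | No: grade columns only |
| Tables 122-123, 158-159, 200-201 (by-parameter CS, other) | No: only parameters without a scale |
| Tables 40/41, row for any CS laboratory abnormality | Yes: from the laboratory eCRF flag, by treatment group and relatedness, no grade condition |
| Tables 62-69 (abnormal results in the CSR body) | Yes: ONR included, with a CS column |
| Listings 15-18 | Yes: CS column |

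**2. One-direction grading (SAP Table 5, the same scale as Protocol Appendix C)**

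Count the graded blood and coagulation tests whose reference range has both a lower and an upper limit.

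- Graded both ways: sodium, potassium, bicarbonate, glucose, calcium, WBC = 6.
- Graded one way, chemistry: BUN, creatinine, albumin, total protein, alkaline phosphatase, AST, ALT, total bilirubin = 8.
- Graded one way, hematology: hemoglobin, lymphocytes, neutrophils, platelets = 4.
- Graded one way, coagulation: prothrombin time, INR, APTT = 3.

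One way: 8 + 4 + 3 = 15. Total: 15 + 6 = 21. Share: 15/21 = 71%.

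eGFR and eosinophils are left out. Their ranges (60 or above; 0.00 to 0.70) have no opposite abnormal direction. Alkaline phosphatase is marked N (not graded) in the direction column but has upward grade limits. Dropping it gives 14/20 = 70%.

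Examples without a grade: platelets above 450, neutrophils above 8.6, lymphocytes above 4.2. In urinalysis the gap is small, because most ranges there have no opposite abnormal direction; urobilinogen (0.2 to 1.0, graded upward only) is an exception.

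**3. Direct bilirubin**

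It is in the Table 120 shell but has no row in SAP Table 5 or 6, and Table 122 lists only cystatin-C. Before v11.0 it has no range-based grade and no other by-parameter CS table.

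**4. Vital signs**

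Table 5 grades systolic pressure and heart rate both ways, but diastolic pressure only upward. A CS diastolic fall has no range-based grade before v11.0. Protocol 8.6.4 lists a diastolic decrease of more than 30% among its infusion-halting signs, so such a fall is not a value the protocol ignores.

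**5. Effect of one omitted participant (illustration)**

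Assume one participant has such a result. Intervals are exact Clopper-Pearson, the method in SAP 6.1; the CS shells themselves show only n and %. For 0/n the upper limit is 1 − 0.025^(1/n). For 1/n the lower limit is 1 − 0.975^(1/n), and the upper limit is the 0.975 quantile of Beta(2, n − 1).

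| Group | As planned | With an ungraded column |
|---|---|---|
| Dose group, n = 6 | 0/6 = 0% (0 to 45.9%) | 1/6 = 16.7% (0.4 to 64.1%) |
| Pooled placebo, n = 10 | 0/10 = 0% (0 to 30.8%) | 1/10 = 10% (0.3 to 44.5%) |

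The split by protocol version can make these denominators smaller.

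**The case against.** **The results are not lost.** A reader might infer that ungraded CS results appear in no table. That is not so: Tables 40/41 count the participants from the investigator's flag, and Tables 62-69 show the values. This stands, and it limits the gap to the by-parameter tables.

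**CS results may carry a grade after all.** Protocol 8.5 has sites note a grade with each CS laboratory abnormality, and Protocol 8.1.1.1 gives general severity guidelines for events outside either scale. CS vital signs are drawn from reported AEs (SAP 9.7), and all AEs are graded, so the vital-sign gap is the less certain part. This stands in part. But SAP 9.6 grades laboratory results by the range tables and labels the rest ONR, SAP 9.7 also points to the range tables, and the SAP never says which grade fills the CS shells.

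**A grade condition has some support.** Protocol 8.2 describes clinically important laboratory changes as a move to a higher grade than at baseline. But the endpoint is worded as clinically significant, the CS shells do not apply that shift rule, and Tables 122-123 count CS results with no grade at all.

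**ECG.** A reader might infer that the third primary endpoint is undercounted. Table 221 counts shifts to abnormal-CS from the overall reading with no grade condition, and no planned table uses the grade-plus-reading rule. Only a conflict of wording remains.

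**Size.** Counting every one-direction row in Table 5 gives 17 of 23, which wrongly includes eGFR and eosinophils. Either figure counts rows of a scale, not expected CS results, and many opposite-direction values may never be called CS. Occult blood is a weak example: microscopy supersedes the dipstick (SAP 4.5.1), and microscopic blood is graded.

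**Conclusion.** The gap is real in the by-parameter displays. If the CS laboratory shells are filled from range-based grades, as SAP 9.6 reads, a CS result without a grade on a scaled parameter is absent from all of them. Before v11.0 this can happen in the ungraded direction of 15 of 21 tests and for any direct bilirubin result. The same holds for a diastolic fall in Table 219 if range-based grades are used there. Each omitted participant is worth 16.7 percentage points in a full dose group, or 10 in pooled placebo.

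The documents do not support two further inferences. A dose-dependent undercount cannot be shown: the CTCAE ranges are not in the documents, so the gap under v11.0 cannot be sized, and SAP 6.7 already presents the two versions separately and warns of differences in laboratory and vital-sign AE counts across treatment groups. Nor is the endpoint left uncounted overall, given Tables 40/41.

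Severity is minor to moderate. The analysis is descriptive, the data are collected, and the participants are counted elsewhere.

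**What to change.** - Add one column, 'CS, ONR/not graded', to Tables 120-121, 156-157, 171-172, 198-199 and 219-220.
- State in SAP 9.6 and 9.7 whether the range-derived or the site-recorded grade feeds these tables.
- Move direct bilirubin to Table 122 for participants enrolled before v11.0.
- Reconcile the SAP 9.8 sentence requiring a toxicity grade with the PI-judgement rule in the same section and in Protocol 7.1. Table 221 needs no change.

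The cost is a few sentences and minor shell edits, with no new data because the CS flag is already on the laboratory eCRF. The downside is that a few more CS results may be shown. The gain is that the parameter tables can be reconciled with the any-CS-laboratory row in Tables 40/41.
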